# 16. Identification and Access to Source Data

#### 16.1 Source Data

Source documents and source data are considered to be the original documentation where subject information, visits consultations, examinations and other information are recorded. Documentation of source data is necessary for the reconstruction, evaluation and validation of clinical findings, observations and other activities during a clinical trial.

#### 16.2 Access to Source Data

The site investigators and site staff will make all source data available to the DAIT/NIAID, as well as to relevant health authorities. Authorized representatives as noted above are bound to maintain the strict confidentiality of medical and research information that may be linked to identified individuals.

Confidential Page 67 of 80

#### 17. Protocol Deviations

#### 17.1 Protocol Deviation Definitions

**Protocol Deviation** – The investigators and site staff will conduct the study in accordance to the protocol; no deviations from the protocol are permitted. Any change, divergence, or departure from the study design or procedures constitutes a protocol deviation. As a result of any deviation, corrective actions will be developed by the site and implemented promptly.

Major Protocol Deviation (Protocol Violation) - A Protocol Violation is a deviation from the IRB approved protocol that may affect the subject's rights, safety, or well-being and/or the completeness, accuracy and reliability of the study data. In addition, protocol violations include willful or knowing breaches of human subject protection regulations, or policies, any action that is inconsistent with the NIH Human Research Protection Program's research, medical, and ethical principles, and a serious or continuing noncompliance with federal, state, local or institutional human subject protection regulations, policies, or procedures.

**Non-Major Protocol Deviation** - A non-major protocol deviation is any change, divergence, or departure from the study design or procedures of a research protocol that does not have a major impact on the subject's rights, safety or well-being, or the completeness, accuracy and reliability of the study data.

### 17.2 Reporting and Managing Protocol Deviations

The study site PI has the responsibility to identify, document and report protocol deviations as directed by the study Sponsor. However, protocol deviations may also be identified during site monitoring visits or during other forms of study conduct review.

Deviations that impact the ability of the Sponsor and PI to assess the study outcomes will be collected for this study. When a deviation is identified, the site will record the deviation on the eCRF. In addition, the site will be responsible to report deviations to the applicable IRB, according to local guidelines.

The SACCC will compile monthly listings of deviations. NIAID, the study PI and DSMB will review deviations on a regular basis. Protocol deviations will also be included in the annual report to FDA.

# 18. Ethical Considerations and Compliance with Good Clinical Practice

# 18.1 Statement of Compliance

This clinical study will be conducted using good clinical practice, as delineated in *Guidance for Industry: E6 Good Clinical Practice Consolidated Guidance*, and according to the criteria specified in this study protocol. Before study initiation, the protocol and the informed consent documents will be reviewed and approved by each site's IRB, NIAID, and FDA. Any amendments to the protocol or to the consent materials will also be approved by the same entities before they are implemented.

#### **18.2 Informed Consent Process**

The consent process will provide information about the study to a prospective participant and will allow adequate time for review and discussion prior to his/her decision. The PI or designee listed on the FDA 1572 will review the consent and answer questions. A physician listed on the 1572 must participate in the consent process. The prospective participant will be told that being in the trial is voluntary and that he or she may withdraw from the study at any time, for any reason. All participants will read, sign, and date a consent form before undergoing any study procedures. Consent materials will be presented in participants' primary language. A copy of the signed consent form will be given to the participant.

The consent process will be ongoing; the consent form will be reviewed with each subject in Cohorts 2, 3, and 4 prior to darTreg infusion. The consent forms will be revised when important new safety information is available, the protocol is amended, and/or new information becomes available that may affect participation in the study.

The consent process must be appropriately documented in the subject's records. A copy of the signed consent forms should be given to each subject.

### 18.3 Privacy and Confidentiality

A participant's privacy and confidentiality will be respected throughout the study. Each participant will be assigned a unique identification number and these numbers rather than names will be used to collect, store, and report participant information. Site personnel will not transmit documents containing personal health identifiers (PHI) except for those lawfully required for manufacture and administration of cell therapies, and to ensure that the appropriate cell product is administered to the intended recipient.

# 19. Publication Policy

The publication guidelines and policies stipulated in the grant will apply to this trial.

Confidential Page 70 of 80

# Appendix 1. Recipient Schedule of Events (Stages 1 and 2)

		STAGE	1							STAGE 1 Stage 2														
	Screen A	PBM C Collection 	Day 0 (Tx) 	Screen B	D2	D3	D4	D5 [	06 W	2 W3	3 W4	Screen		W6	W 7	W8 W	/9 W1	0W1	1W12	W13	W14V	N16V	V18W2	Clinically 0 Indicated Bx/ Rejection
/isit Number	Screen A	1	2	Screen B	3a 	3b	4	5a 5i	o  6	7	8	Screen (		10	11	12 1	3 14	15	15a 	15b 	15c  1	15d  1	5e 13 15f	
/isit Window	- 6 Months		-3mons				None									+/-2 da								N/A
		St	tudy As	sessment	ts																			
nclusion Criteria and Exclusion Criteria A	х	х																T			$\overline{}$	7.		
nclusion Criteria and Exclusion Criteria B				х																	$\overline{}$	$\overline{}$		1
nclusion Criteria and Exclusion Criteria C												x 									7	7		1
nformed Consent	х																	T			7	7		1
Demographics (DOB, Gender, Ethnicity)	Х																	1			7	7		1
Medical History	х																	T			7	7		1
Physical Examination	х					х			×	х	х						x12	2			7	7		×
HCC Assessment, Pathology, Treatment	х		х															T			7	7		1
Review/Collect Current Immunosuppressive and Anti-Infective Medications			$\rightarrow$			→	$\rightarrow$	→ /	$\rightarrow$	·	→	$\rightarrow$	$\rightarrow$	$\rightarrow$	→	→ -	→ →	_	4	4	4	4	4 4	×
Adverse Event/Serious Adverse Event Assessment		x 				$\rightarrow$	$\rightarrow$	→ /	$\rightarrow$	· -	→	$\rightarrow$	$\rightarrow$	$\rightarrow$	→	→ -	→ →	_	4	4	4	4	4 4	×
	Investiga	tional Agents	and Im	nmunosup	press	sive M	/ledicat	tions																
PBMC Collection (450ml Phlebotomy 1 or Leukapheresis for Cohort 2, Leukapheresis for Cohorts 3 and 4)		х																				 		
Solumedrol 500 mg			x 																		=	7.		1
Prednisone Taper			$\rightarrow$	$\rightarrow$		→	$\rightarrow$	→ /	$\rightarrow$	· -	$\rightarrow$	$\rightarrow$	$\rightarrow$	Disc	ontinue	steroid	s bv w	eek 5			=	7.		1
MMF (Cellcept 500 mg BID or Myfortic 360 mg BID)			х	х		х	x	x	×	x	×	х	D/c M	MF once	e EVR ta	rget trou	ah is rea	ched.	5		7	7	//	1
- Facrolimus						Initia	ate w ithi	in 72 hr	s of tx.	target	t trough	1 6-8 µg/L 					C targ		ah 3-5	ua/L 		Ť		
Trymoglobulin® Infusion (3-4.5 mg/kg)					First		within 72			T	T			П		Т	T	Т			$\overline{}$	$\supset$		1
VR Conversion										1						EVI	R target	trouc	h 6-8 µ	a/L 2, !	,	Ť		Ī
darTreg Expansion (Cohorts 2, 3, and 4 Only)										$\top$	1			П					Х	Ĭ1				1
		Local L	aborato	ry Assess	sment	ts																		
Pregnancy Test (Urine or Serum hCG)				2														T			$\overline{}$	7.		
HLA Typing	х																				7	7		1
Viral Serology: HIV Ab, CMV IgG, EBV IgG, HBV (HBsAg, HBcAb, HBeAb, HBeAg, HDVAb), HCVAb3	х																				7	7.		1
/iral Nucleic Acid Testing: HBV DNA (for HBV positive subjects)	х	х																			=	7.		1
Viral Nucleic Acid Testing: HCV NAT (Screen A: most current test within 6 months prior to txp, Screen C: all subjects)	Х			х								х									7	$\overline{}$		1
CBC (with differential and platelets)	х		x 	х		х	х	x	×	х	х	х	х	х	х	x >	( X	х	X	X	X	X	x x	×
CD3 Count					x10	х	х	x x	10									T			7	7		1
CD4 Count												х						T			7	7		
Basic Chemistry (Na, K, Cl, CO2, Creatinine, BUN)	х		x 	х		х	х	x	×	х	х	х	х	х	х	x >	( X	х	X	X	X.	X	x x	×
Liver Function Tests (ALT, AST, Alk Phos, GGT, T Bilirubin, D Bilirubin)	х		x 	х		х	х	x	×	х	х	х	х	х	х	x >	( X	х	X	X	X	X	XX	X
NR/PTT	х		x 	х		х	х	x	×	х	х	х	х	х	х	x )	( X	х	X	X	X	X	XX	x
AFP 	х		x 																		7	7		1
Facrolimus Level									×	х	х	х	Х	х	х	x >	( X	х	X	X	X	$\mathbf{x}$	XX	×
EVR Level 														х	Х	x )	СХ	х	X	X	X	X.	XX	x
Jitrasound and Doppler Examination												х									7	7		1
Jrine Protein/Creatinine Ratio												х									7	7		1
ocal Pathology Results - Graft Routine Histology			x 															x 13	3		1	7		×
		Central I	Laborato	ory Asses	smer	nts																		
rotocol Liver Biopsy																		x 13	3		$\overline{}$			×
reg TruCount (2ml Green Heparin Tube)	2																					$\overline{}$		Collect only w
Allofrequency Assay & MFC-Leukocyte, Treg, Tact/mem, B Cell Panels (10 ml Green Heparin Tube)			10 							$\top$		10						1			7	7		CIB visit
/ILR Suppression Responder Cells (10-10 ml Green Heparin Tubes)			100							$\top$								1			7	7		coincides w
MLR Suppression (2-10ml Green Heparin Tubes)			20 							$\top$		20						1			7	7		scheduled vi
Alloantibody Analysis-Donor HLA Ab (3ml Serum Separator Tube)	1		3 			$\Box$				$\top$							1	$\top$			$\nearrow$	$\nearrow$	$\overline{}$	with central la
and the state of t	2																							

PBMC Collection Visit does not apply to Cohort 1. Cohort 2 can have whole blood collection for PBMC isolation if hemoglobin is ≥10.5 mg/dl; leukapheresis if <10.5 mg/dl.

<sup>2 Screening for eligibility C1 and C2 can be assessed between 5-6 weeks (30-44 days) after transplantation. Everolimus can be started on or after 30 days after liver transplantation if eligibility criteria are met (Screen C1).

 $^3\mbox{HIV/HBV/HCV}$  serology can be within one year of screening.

<sup>4AFP is only required for subjects known to have HCC. At Screen A, AFP should be drawn if unavailable within 3 preceding months; AFP should be redrawn at time of transplant. After transplant, AFP should be recorded every 3 months.

<sup>5 First EVR level should be obtained within one week of first dose (+/- 2 days). MMF discontinuation and TAC trough 3-5 μg/L for subjects converting to EVR only. Subjects continuing on TAC-based IS should have troughs 6-8 μg/L.

<sup>6 Prior to Thymoglobulin, collect AE's/SAE's occurring within 72 hours after PBMC Collection only. Collect all AE's/SAE's grade 2 and higher from the time of first Thymoglobulin infusion.

<sup>7 Central laboratory assessments may be drawn up to one year BEFORE solumedrol dose in OR. Once drawn, mechanistic labs do not need to be repeated.

<sup>8CBC, Basic Chemistry, Liver Function Tests, and PT/INR/PTT should be collected as close to, but prior to transplant as possible.

<sup>9Liver allograft biopsy should be obtained prior to transplantation (back table) for local pathology reading only, no specimen for central pathology

<sup>10 Screening should take place within 24 hours prior to Thymoglobulin®. The first dose of Thymoglobulin® is to be given within 72 hours after transplantation. Additional doses of 0.75-1.5 mg/kg IV will be administered until CD3 count is ≤50 cells/μL (50 cells/mcL) or total lymphocyte count is ≤ 0.10 x 10 ½L; or when maximum dose of 4.5/mg/kg has been given. Day 2 and Day 6 visits are only needed if Thymoglobulin is given on these days.

 Treg expansion should be initiated 2-3 weeks prior to planned Treg infusion if subjects continue to meet eligibility criteria. Please refer to Stage 3 Schedule of Events. .

 Visits to the transplant center are required for physical exams. A transplant center visit and physical exam is not required for Cohort 1 at Week 10; physical exam and transplant center biopsy visit between Week 10-14 for Cohorts 2, 3, and 4 only.

<sup>13Subjects in Cohorts 2, 3, and 4 should have protocol biopsy between week 10 and 14 to assess eligibility D for Stage 3 (See Stage 3 SOE). Subjects in Cohort 1 should have a protocol biopsy at week 12 after transplant (See Stage 2 Follow Up). Visits 15a-15f should be conducted to collect weekly labs if subject has not started Stage 3 SOE.

 Local laboratory assessments collected (retrospective chart review) at the time of clinically indicated biopsy should reflect reason for biopsy (e.g. elevated LFTs).

Time after Transplant	W12	W20	W24	W28	W32	W36	W40	Clinically Indicated
Time after darTregs**	T0**	T56**	T84**	Tw16**	Tw20**	Tw24**	Tw28**	Biopsy/ Rejection
Visit Number	16	18	19	20	21	22	23	CIB/ Rej.
Visit Window	-14/+10 days							Within -14 days of study visit
Study Assessments								
Physical Examination	Х						Х	Х
Review/Collect Current Immunosuppressive and Anti-Infective Medications	$\rightarrow$	$\rightarrow$	$\rightarrow$	$\rightarrow$	$\rightarrow$	$\rightarrow$	$\rightarrow$	Х
Concomitant Medications (inlcuding treatment for rejection and HBV)	$\rightarrow$	$\rightarrow$	$\rightarrow$	$\rightarrow$	$\rightarrow$	$\rightarrow$	$\rightarrow$	Х
Adverse Event/ Serious Adverse Assessment	$\rightarrow$	$\rightarrow$	$\rightarrow$	$\rightarrow$	$\rightarrow$	$\rightarrow$	$\rightarrow$	Х
Investigational Agents and Immunosuppre	ssive Me	edication	S					
Tacrolimus Maintenance		٦	AC targ	et trougl	h 3-5 µg/	L		
EVR Maintenance	EVR tar	get trough	6-8 µg/L	EV	R target tr	ough 4-6 l	µg/L	
Local Laboratory Assessment	ents							
HBV DNA and HBsAb Quantitative	Х							
HCV RNA (for previously HCV positive subjects only)	Х							
CBC (with differential and platelets)								Х
CD4 Count	Х		Х				Х	
Basic Chemistry (Na, K, Cl, CO2, BUN)	Х	Х	Х	Х	Х	Х	Х	Х
Liver Function Tests (ALT, AST, Alk Phos, GGT, T Bilirubin; D Bilirubin)	Х	Х	Х	Х	Х	Х	Х	Х
INR/PTT	Х							
AFP 	Х		Х				Х	
Tacrolimus Level	Х	Х	Х	Х	Х	Х	Х	Х
EVR Level	Х	Х	Х	Х	Х	Х	Х	Х
Local Pathology Results - Graft Routine Histology								Х
Central Laboratory Assessm	ents							
Protocol Liver Biopsy 	Х							Х
Allofrequency Assay & MFC-Leukocyte, Treg, Tact/mem, B Cell Panels (10 ml Green Heparin Tube)	10		10				10	Collect only when
MLR Suppression (2-10ml Green Heparin Tubes)	20		20				20	CIB visit coincides
Treg Detection: TCR Sequencing (10ml Green Heparin Tube)	10		10				10	with scheduled
Alloantibody Analysis-Donor HLA Ab (3ml Serum Separator Tube)	3		3				3	visit with central
	43.0		43.0				43.0	

\*\* Corresponds with Cohorts 2, 3, and 4 time points (post drTreg infusion).

<sup>1For each protocol (W12) or clinically indicated biopsy, one specimen will be in formalin for unstained slides, one specimen in PBS for deuterium tracking, and one specimen in RNALater.

<sup>2AFP is only required for subjects known to have HCC.

Confidential Page 77 of 80

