#### 4.3 Exclusion Criteria

#### 4.3.1 Screening and Enrollment Exclusion Criteria A (Stage 1)

Below are exclusion criteria to be assessed at study enrollment, prior to **Stage 1 study procedures**. Subjects who meet any of these criteria are ineligible for study participation.

- End stage liver disease secondary to autoimmune etiology (autoimmune hepatitis, primary biliary cirrhosis, or primary sclerosing cholangitis)
- 2. History of less than 5 years remission of malignancy, except for 1) HCC or 2), history of adequately treated in-situ cervical carcinoma, or adequately treated basal or squamous cell carcinoma of the skin
- 3. History of previous organ, tissue or cell transplant
- 4. Serologic evidence of human immunodeficiency 1 or 2 infection
- 5. Epstein Barr Virus (EBV) sero-negativity (EBV naïve candidates)
- 6. Cytomegalovirus (CMV) sero-negativity (CMV naïve candidates) if donor is positive
- 7. Chronic use of systemic glucocorticoids or other IS, or biologic immunomodulators
- 8. Chronic condition requiring anti-coagulation after liver transplantation
- 9. Any chronic illness or prior treatment which, in the opinion of the investigator, precludes study participation
- 10. Participation in any other studies that involved investigational drugs or regimens in the preceding year
- 11. Received any vaccination within 28 days prior to leukapheresis or blood collection for Treg manufacture
- 12. Hemoglobin < 9.0 g/dL within 10 days prior to screening
- 13. Neutrophils <1,500/μL within 10 days prior to screening
- 14. Platelets <40,000/μL within 10 days prior to screening

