# 8. Study Mandated Procedures

# 8.1 Leukapheresis or Whole Blood Draw for PBMC Collection

Leukapheresis may be necessary to ensure collection of adequate numbers of autologous Tregs to support ex vivo expansion of darTregs for infusion after liver transplantation, particularly for those enrolled in Cohorts 3 and 4. The study team will make a decision in the best interest of a particular subject based on the current clinical picture including assigned study cohort, peripheral Tregs in circulation, and hemogloblin level. If a subject has a hemoglobin level greater than 10 gm/dL, he or she will have the option to undergo phlebotomy. If the patient has a hemoglobin level less than or equal to 10 gm/dL and remains eligible for the study, the patient will undergo leukapheresis. Number of Tregs in peripheral circulation will also guide decision for method of PBMC collection (leukapheresis or whole blood) where subjects should have at least  $30/\mu$ L peripheral blood Tregs for whole blood collection. For subjects to have whole blood draw, 450-500ml whole blood will be collected.

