#### 9.4.2 Risks of Blood Draw

Risks of blood draw or venipuncture are typically minimal with temporary local discomfort. More serious risks would include ecchymosis and, rarely, localized infection. The amount of blood that may be drawn from adult subjects for research purposes will not be more than 168 mL over an eight-week period. The additional amount of blood could contribute to the development of anemia. The subject's clinical condition will be taken into consideration to determine if research blood tests can be performed.

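### For Cohort 2 whole-blood collection, Section 8.1 and Appendix 1 give different hemoglobin cut-offs (10 versus 10.5), and Section 9.4.2 does not say whether its 168 mL limit covers that draw

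*Protocol*

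**What the plan says.** Protocol Section 8.1 sets the choice of collection method. On the upper side it says "If a subject has a hemoglobin level greater than 10 gm/dL, he or she will have the option to undergo phlebotomy". On the lower side it says "If the patient has a hemoglobin level less than or equal to 10 gm/dL and remains eligible for the study, the patient will undergo leukapheresis". It leaves the decision to the study team, in light of cohort, circulating Tregs and hemoglobin, and asks for at least 30 Tregs per µL before whole blood is used. On volume: "For subjects to have whole blood draw, 450-500ml whole blood will be collected".

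Footnote 1 of Appendix 1, the schedule that sites work from, says: "Cohort 2 can have whole blood collection for PBMC isolation if hemoglobin is ≥10.5 mg/dl; leukapheresis if <10.5 mg/dl". Its opening words, "Cohort 2 can have whole blood collection for PBMC isolation if hemoglobin is", tie the whole-blood rule to that cohort. The same schedule gives the draw volume as "PBMC Collection (450ml Phlebotomy", which lies within the range in Section 8.1.

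Other hemoglobin thresholds are in grams per decilitre, for example the entry exclusion in Section 4.3.1: "Hemoglobin < 9.0 g/dL within 10 days prior to screening".

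Section 9.4.2, on the risks of blood draws, says that blood taken from adult subjects for research "will not be more than 168 mL over an eight-week period". It names no exemption.

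**The concern.** The hemoglobin rule decides whether a waitlisted patient with end-stage liver disease may have about half a litre of blood taken. Two current passages give different thresholds, and neither says which governs. A site that follows Section 8.1 could be recorded as deviating from Appendix 1, since Section 17.1 counts any departure from the study procedures as a deviation. The unit in the footnote is also not the one used for hemoglobin elsewhere.

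The 168 mL statement raises a second question. The collection is listed among the study-mandated procedures and is called protocol mandated in Section 14.4.1. The Study Definitions describe such procedures as performed solely for the research. On a plain reading, a 450-500 mL research draw and a 168 mL limit on research blood do not fit together.

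**Working it through.** **Hemoglobin cut-off.** Inputs: the two sentences in Section 8.1, footnote 1 of Appendix 1, and the entry limit in Section 4.3.1. With the footnote read in g/dL:

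| Hemoglobin (g/dL) | Section 8.1 | Appendix 1, footnote 1 | Agree? |
|---|---|---|---|
| 9.0 to 10.0 | leukapheresis | leukapheresis | yes |
| above 10.0, below 10.5 | phlebotomy optional | leukapheresis | no |
| 10.5 and above | phlebotomy optional | whole blood allowed | yes |

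The entry limit excludes only values below 9.0 g/dL, so the middle row can occur among enrolled subjects.

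**Who is affected.** Section 5.1.1, Section 10.1 and Appendix 1 confine whole-blood collection to Cohort 2. Cohorts 3 and 4 have leukapheresis, and Cohort 1 has no PBMC collection visit. The synopsis puts Cohort 2 at 3 to 6 subjects. The documents give no hemoglobin distribution, so the number in the band could be anywhere from none to all of them, plus any replaced subjects.

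**Unit.** Taken literally, 10.5 mg/dL = 10.5 / 1000 = 0.0105 g/dL. Every enrolled subject would exceed that, so the footnote would direct nobody to leukapheresis. It is an evident typing error for g/dL.

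**The 168 mL limit.** If it covered the manufacturing draw:
- 450 / 168 = 2.68 times the limit, an excess of 450 − 168 = 282 mL.
- 500 / 168 = 2.98 times the limit, an excess of 500 − 168 = 332 mL.

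The protocol does not derive the 168 mL, so it cannot be reproduced. It can be compared with the scheduled central-laboratory tubes:
- Appendix 1, legible entries: 2 mL at Screen A; 10 + 100 + 20 + 3 = 133 mL at Day 0; 10 + 20 = 30 mL at Screen C. Total 2 + 133 + 30 = 165 mL.
- Appendix 3, printed column totals from infusion to day 28: 43 + 20 + 50 + 50 = 163 mL.

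Both totals fall just under 168 mL. Two cautions apply. The tables are partly broken in the text available. In particular, the infusion-day entries in Appendix 3, as they can be read, add to 10 + 20 + 10 + 10 + 3 = 53 mL, not the printed 43, which would make the second total 173 mL. Also, the Appendix 1 total falls within one eight-week window only for some timings of Screen A and of the Day 0 tubes, which may be drawn early.

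**The case against.** On hemoglobin, the best defence is that Section 8.1 is permissive. Above 10 g/dL it gives an option, subject to the study team's judgement and the Treg count. A team that chooses leukapheresis between 10.0 and 10.5 complies with both passages, so the conflict arises only if phlebotomy is chosen there. That is right and narrows the point, but it leaves two different thresholds for offering the draw.

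On volume, a reader might infer that the design cannot meet its own safety limit. The documents do not establish that. Section 8 treats PBMC collection (8.1) apart from blood draws (8.2), and Section 9.4.2 takes its title from the latter. Appendix 1 lists PBMC collection with the investigational agents and the research tubes under central laboratory assessments. Section 12 separates blood for manufacturing from samples taken only for mechanistic studies. The tube totals sit close to 168 mL. A limit on mechanistic tubes is therefore the more natural reading.

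What survives is that Section 9.4.2 does not say so. Section 14.3.2 expressly sets the 450-500 mL draw apart when it exempts blood draws from adverse event reporting, so the authors wrote an exception where they wanted one. Section 9.4.1 covers leukapheresis only. If Section 9.4.2 leaves the large draw out, no risk section addresses it.

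A reader might also infer consequences for the anemia outcome, or for exclusions under Criteria B at hemoglobin below 8.0 g/dL. The draw can happen at any time before transplantation. The safety outcomes count events within 40 weeks of transplantation, and Criteria B is assessed after surgery, before Thymoglobulin. Nothing in the documents links the draw to either.

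**Conclusion.** The inconsistency is real and minor. For Cohort 2 subjects with hemoglobin above 10.0 and below 10.5 g/dL, Section 8.1 permits the offer of a 450-500 mL draw that Appendix 1 does not allow. This assumes that the footnote means g/dL, which the protocol's other hemoglobin thresholds support. The conflict does not extend to other cohorts, and the unit error is unlikely to mislead a site in practice.

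The 168 mL point is a request for clarification. The ratios of 2.68 and 2.98 matter only if the limit was meant to include the manufacturing collection, and the protocol's structure suggests that it was not. No estimate, confidence interval, stopping threshold or sample-size figure depends on either point.

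**What to change.** Reconcile Section 8.1 and footnote 1 of Appendix 1 to a single hemoglobin cut-off in g/dL, including what happens at the cut-off itself. The value is for the sponsor to decide; this review takes no position on it. Correct the unit in the footnote.

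In Section 9.4.2, state whether the 168 mL limit covers mechanistic tubes only or also the manufacturing collection, so that it does not conflict with Section 8.1. If the manufacturing draw is outside the limit, say where its risks are described.

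The cost is protocol wording only, with a check that site materials carry the same text. The SAP needs no change.
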